9.3.1. Inclusion Criteria

[figure not shown]
Evidence of a personally signed and dated informed consent document indicating that the patient (or a legally acceptable representative) has been informed of all pertinent aspects of the study.

Participants who meet all the following criteria will be eligible for enrollment in this study:

1. Willing and able to provide written informed consent (aged ≥ 18 years), parental/guardian consent and participant assent (aged ≥ 12 to <18 years) per local regulations, or pediatric participants (aged 4 to <12 years) with parental/guardian consent per Institutional Review Board (IRB) policy and requirements, consistent with ICH guidelines
2. Male or female participants with documented diagnosis of sickle cell disease (all genotypes)
3. Participants who are currently taking Oxbryta® (Voxelotor) or have been prescribed and will initiate treatment with Oxbryta® (Voxelotor) according to the Oxbryta® (Voxelotor) USPI

When participants have been prescribed Oxbryta® (Voxelotor) and deemed eligible to participate in the registry study based on the inclusion/exclusion criteria, they will be enrolled in the study regardless of whether they have started taking Oxbryta® (Voxelotor). After enrollment into the study, it is recommended that the site perform the pre-Oxbryta® (Voxelotor) participant assessments as soon as possible. Once the first dose of Oxbryta® (Voxelotor) treatment has been administered, the participants will be followed for up to 5 years. Patient enrollment process flow is in [Figure 2](#).

Figure 2. Enrollment Process Flow

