10.3.5. Physical Examination

Height and weight will be collected at the screening visit for all participants of age 18 and above, and at screening and all follow up visits for participants up to age 18. Pulse oximetry [%SpO₂] will be collected for all participants at screening and all follow up visits per SOC.

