10.3.6. Effectiveness Data

10.3.6.1. Clinical Outcomes

10.3.6.1.1. Laboratory Assessments

The following data will be recorded on the CRF:

For pre-Oxbryta® (Voxelotor) Treatment Visits, only the most recent results from regularly scheduled outpatient visit will be entered.

For post-Oxbryta® (Voxelotor) Treatment Regularly Scheduled Outpatient Visits, all available results during the data collection period will be entered.

For post-Oxbryta® (Voxelotor) Acute Visits (Emergency Department, Hospitalization, Acute Pain/Infusion Center), only the results on the day of presentation (or first available results during the visit) and day of discharge will be entered, if available.

The following data from the most recent results will be recorded in the CRF:

- Hb (including % HbF at baseline and all follow up visits), white blood cells (WBC), absolute neutrophil count (ANC), mean corpuscular volume (MCV), mean corpuscular hemoglobin concentration (MCHC), Platelets, aspartate aminotransferase (AST), alanine aminotransferase (ALT), and lactate dehydrogenase (LDH).
- Hemolysis measures, including % reticulocytes, absolute reticulocytes, bilirubin (total, direct, and indirect)
- Measures of iron overload (ferritin, iron, TIBC, T2*MRI)
- Creatinine (Serum)
- Albuminuria (urine albumin/creatinine ratio [ACR])
- Hemoglobinuria (urine dipstick positive for blood +1 or greater and ≤ 2 RBC by high power field)
- Serum cystatin C
- eGFR calculated using CKD-EPI equation

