10.3.6.1.8. Other SCD Complication

Data on other SCD complications will be collected. This may include sickle cell anemia, splenomegaly/splenectomy, dactylitis, cholelithiasis/cholecystectomy, aplastic crisis, chronic or end stage kidney disease (as defined by GFR <60), iron overload (as diagnosed by T2* MRI or R2* MRI), pneumonia, retinopathy, avascular necrosis, deep vein thrombosis, and chronic/acute pain.

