4. RESEARCH METHODS

4.1. Study design

This registry is an observational study designed to evaluate the effect of Oxbryta® (Voxelotor) in individuals with SCD. This registry is intended to benefit and support interests of participants, clinicians, regulatory bodies, payers, and industry by obtaining longitudinal data on Oxbryta® (Voxelotor). Approximately 500 participants with SCD who are prescribed and treated with Oxbryta® (Voxelotor) will be enrolled. The study will be conducted at approximately 35 sites in the US.

Any participant who is currently taking Oxbryta® (Voxelotor) or has been prescribed and will initiate treatment with Oxbryta® (Voxelotor), is eligible to participate. Eligible participants will receive treatment with Oxbryta® (Voxelotor) as prescribed by their physicians, as part of their usual care. Participants will be treated and evaluated per standard of care (SOC) and at the physician's discretion.

Participants will be introduced to the study by their health care team and will sign the informed consent form (ICF) or assent prior to any data collection for the study.

[figure not shown]
This study will collect data that are recorded in the participants' medical records and other secondary data sources such as Insurance and Pharmacy Claims. Study data will be collected at regular intervals (no more frequent than every 3 months) and entered in case report forms (CRFs) via an electronic data capture (EDC) system by the study staff.

Regardless of how long participants have been on Oxbryta® (Voxelotor) when they enroll in the study, participants will be followed for up to 5 years after their first dose of Oxbryta® (Voxelotor) treatment, or until they withdraw their consent to participate, or are discontinued from the study. Treatment, including interruptions and restarting treatment, will continue at the discretion of the treating physician, and there are no pre-defined treatment requirements. Participants may receive any additional medications prescribed by their treating physician or have any medical interventions that are deemed appropriate by the treating physician or study doctor. The participant or treating physician may discontinue Oxbryta® (Voxelotor) at any time. Participants who discontinue treatment with Oxbryta® (Voxelotor) earlier than 5 years will continue to be followed on study to collect clinical and health-related quality of life (HRQoL) outcomes for up to 5 years after their first dose of Oxbryta® (Voxelotor) treatment.

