Bilirubin (Direct)	Effectiveness endpoint measures - Chemistry	Case report form	Captured from laboratory assessment-Chemistry form

Bilirubin (Indirect)	Effectiveness endpoint measures - Chemistry	Case report form	Captured from laboratory assessment-Chemistry form
Ferritin	Effectiveness endpoint measures - Chemistry	Case report form	Captured from laboratory assessment-Chemistry form
Albumin Creatinine Ratio (ACR)	Effectiveness endpoint measures – Renal function	Case report form	Captured from laboratory assessment- Renal function form
GFR	Effectiveness endpoint measures – Renal function	Case report form	Captured from laboratory assessment- Renal function form
Creatinine (Serum)	Effectiveness endpoint measures – Renal function	Case report form	Captured from laboratory assessment- Renal function form
Serum cystatin C	Effectiveness endpoint measures – Renal function	Case report form	Captured from laboratory assessment- Renal function form
Estimated eGFR	Effectiveness endpoint measures – Renal function	Case report form	Captured from laboratory assessment- Renal function form
Transfusions	Safety endpoint measures	Case report form	Captured from transfusions form
Patient Global Impression of Change (PGI-C)	Effectiveness endpoint measures	Case report form	Captured from Patient Global Impression of Change (PGI-C) form
Clinical Global Impression of Change (CGI-C)	Effectiveness endpoint measures	Case report form	Captured from Clinical Global Impression of Change (CGI-C) form
Pregnancy Testing and Fertility	Safety endpoint measures	Case report form	Captured from Pregnancy Testing and Fertility form
SCD Complications/Adverse Events	Safety endpoint measures	Case report form	Captured from SCD Complications/Adverse Events Question form
Pregnancy	Safety endpoint measures	Case report form	Captured from Pregnancy Notification and Outcome forms
Oxbryta Physician Administration	Exposure measures	Case report form	Captured from Oxbryta Physician Administration form

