- Change from pre-Oxbryta treatment period in the following Chemistry parameters corresponding to treatment with Oxbryta® (Voxelotol):
 - Ferritin

Analysis: Observed and change from pre-Oxbryta treatment period on ferritin will be summarized descriptively ([Section 4.7](#)) by visit.

- Change from pre-Oxbryta® (Voxelotol) treatment period in renal function:
 - Creatinine (Serum)
 - Albuminuria (urine albumin/creatinine ratio [ACR])
 - Hemoglobinuria (urine dipstick positive for blood +1 or greater and ≤ 2 RBC by high power field)
 - Serum cystatin C
 - Estimated eGFR calculated using the CKD-EPI equation

Analysis: Observed and change from pre-Oxbryta treatment period on Creatinine (Serum), Albuminuria, Hemoglobinuria, Serum cystatin C and eGFR will be summarized descriptively ([Section 4.7](#)) by visit

- Rate of SCD complications including acute pain crisis, acute chest syndrome

(ACS), priapism, stroke, and transient ischemic attack (TIA), chronic or end stage kidney disease, iron overload, leg ulcers, cardiac malfunction, and pulmonary hypertension (PH) and RBC transfusions.

Analysis:

The number and percentage of participants with SCD complications including acute pain crisis, ACS, priapism, stroke, chronic or end stage kidney disease iron overload, leg ulcers, cardiac malfunction and PH and RBC transfusions will be summarized by SOC and PT throughout the treatment period.

The annualized incidence rate of SCD complications including acute pain crisis, ACS, priapism, stroke, chronic or end stage kidney disease iron overload, leg ulcers, cardiac malfunction and PH and RBC transfusions will be summarized by SOC and PT throughout the treatment period.

- **PGIC**

PGIC includes 7 response categories: Very much improved, much improved, minimally improved, no change, minimally worse, much worse and very much worse.

Analysis: The PGIC will be summarized as numbers and percentages by visit for each response category.

- **CGIC**

CGIC includes 7 response categories: Very much improved, much improved, minimally improved, no change, minimally worse, much worse and very much worse.

Analysis: The CGIC will be summarized as numbers and percentages by visit for each response category.

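### CKD-EPI is the only eGFR equation named, with no version, marker or age limit, although enrolment starts at age 4 and the renal table pools all ages

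*SAP*

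**What the plan says.** - **Equation.** SAP 4.7.3 lists "Estimated eGFR calculated using the CKD-EPI equation" among the renal endpoints, and Protocol 10.3.6.1.1 has "eGFR calculated using CKD-EPI equation". The endpoint lists in Protocol 8.1.1.2 and SAP 3.2 agree. None of these places gives a version, a marker (creatinine or cystatin C), or a separate rule for children.
- **Population.** Protocol 9.3.1 admits "pediatric participants (aged 4 to <12 years) with parental/guardian consent". SAP 4.1 states that "participants will be followed for up to 5 years after their first dose of Oxbryta® (Voxelotor) treatment", so a child can be observed over years of growth.
- **Analysis.** SAP 4.7.3 states that "Creatinine (Serum), Albuminuria, Hemoglobinuria, Serum cystatin C and eGFR will be summarized descriptively", as observed values and change by visit. SAP Appendix 6.1 gives one full-analysis-set table, 15.2.4. None of the subgroups in SAP 4.2.1 or 4.7.5 is defined by age.
- **Source of the value.** SAP 4.3 has separate rows for GFR and for estimated eGFR, both "Captured from laboratory assessment- Renal function form". SAP 4.7.3 describes the same quantity as calculated.
- **Height.** Protocol 10.3.5 collects height in minors "at screening and all follow up visits for participants up to age 18", but in adults at screening only.

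**The concern.** A creatinine-based equation with age and sex but no height term cannot distinguish a low creatinine caused by small body size from a high filtration rate. Three distortions would then be expected in children: values that are too high, a true loss that looks smaller than it is, and an apparent decline as creatinine rises with growth.

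This matters because change in eGFR is a stated effectiveness endpoint, and SAP 4.7.3 says the abbreviated report concentrates on haematologic and renal laboratory parameters. A pooled table would mix these values with those of adults, and the reader would have no means of separating them. The documents already contain the input that a height-based method needs, but the renal plan does not use it.

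**Working it through.** The documents give no eGFR value, creatinine level, body size or number of children, so there is no stated figure to reproduce. The check is an illustration on declared assumptions.

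**Assumed inputs (not in the documents)**
- Creatinine CKD-EPI 2021: 142 × min(Scr/k, 1)^a × max(Scr/k, 1)^−1.2 × 0.9938^age, × 1.012 if female; k = 0.9 and a = −0.302 (male), k = 0.7 and a = −0.241 (female).
- Height-based comparator (bedside Schwartz): 0.413 × height / Scr.
- Heights: 127 cm at age 8; 115, 133 and 143 cm at ages 6, 9 and 11; 102 cm at age 4; 174 cm at age 17.

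**1. Damping of a true loss (age 8, 127 cm)**
- Height-based 130 implies Scr = 0.413 × 127 / 130 = 0.403. Height-based 65 implies Scr = 0.413 × 127 / 65 = 0.807.
- Boy: 142 × (0.403/0.9)^−0.302 × 0.9938^8 = 172, and with 0.807 it is 140. A 50% loss appears as 19%.
- Girl: 142 × (0.403/0.7)^−0.241 × 0.9938^8 × 1.012 = 156. With 0.807, which lies above her k, it is 115. A 50% loss appears as 26%.

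**2. Apparent fall with growth (height-based value held at 130)**

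| Age, height | Scr | Boy | Girl |
|---|---|---|---|
| 6, 115 cm | 0.365 | 179.6 | 161.9 |
| 9, 133 cm | 0.423 | 168.7 | 153.5 |
| 11, 143 cm | 0.454 | 163.0 | 148.9 |

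The change over ages 6 to 9 is −10.9 (boy) and −8.5 (girl). Over ages 6 to 11 it is −16.6 and −13.0. True function is constant throughout.

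**3. Level, and where the overstatement stops** (range over the 2009 and 2021 creatinine versions and both sexes)

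| Height-based value | CKD-EPI at age 4 | CKD-EPI at age 17 |
|---|---|---|
| 60 | 139 to 152 | 67 to 91 |
| 150 | 175 to 221 | 142 to 162 |

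At age 17 with a height-based value of 150, the difference runs from −8 to +12, so overstatement is not universal.

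**4. Sensitivity to the assumptions**
- A 25% loss (120 to 90) at fixed age, male coefficients, appears as about 8% (2021) or 11% (2009). This is unchanged when 0.413 is replaced by values from 0.35 to 0.45.
- In a cystatin C version, creatinine and height do not enter. At a fixed cystatin C of 0.8 mg/L (male) the value moves only from 131 at age 4 to 124 at age 17, so the growth effect largely disappears.

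**The case against.** The strongest reply is that the documents do not establish which equation is actually used for a child. Version and marker are unstated, cystatin C is collected, and SAP 4.3 says the value is taken from a form. Under Protocol 9.7, sites enter standard-of-care results and leave other fields blank, so a laboratory may already report a paediatric estimate. This stands, and it limits the numbers above to the case where a creatinine version is applied to minors. It does not remove the gap: read literally, the rule is CKD-EPI at every age, and if reported values are used, the equation may differ between sites and visits.

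A second reply concerns weight. eGFR is one of five descriptive renal measures with no hypothesis test, and creatinine, cystatin C and ACR are summarised separately. This stands and lowers the severity.

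A third concerns duration. The indication for ages 4 to 11 dates from December 2021 and SAP version 3 from January 2025. If the data cut is near that date, which is an inference, labelled exposure under age 12 is about three years, and the ages 6 to 9 figures are the fairer ones.

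Two stronger readings are tempting. A reader might infer that the kidney-disease cut-off in Protocol 10.3.6.1.8, "chronic or end stage kidney disease (as defined by GFR <60", becomes almost unreachable in children. The documents do not link this eGFR to that event: SAP 4.7.4 identifies SCD complications from an answer on the complications/AE form. A reader might also infer that every child's renal function is overstated and that the pooled result is biased in a known direction. Step 3 contradicts the first part. On the second, damping and growth act in opposite directions on a measured decline, and the share of children is not given.

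**Conclusion.** The specification gap is certain: a single equation, with version, marker and age range unstated, serves a registry that enrols from age 4, and its results are pooled across ages. The consequences are conditional on a creatinine version being applied to minors. In that case, on the assumed equations and heights, younger children's values are too high, a halving of GFR at age 8 appears as a fall of 19% (boy) or 26% (girl), and stable function appears to fall by about 8 to 11 mL/min/1.73 m² over ages 6 to 9, or 13 to 17 over ages 6 to 11. The effect on the pooled means of Table 15.2.4 can be neither signed nor sized from the documents. Severity is moderate.

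**What to change.** In SAP 4.7.3, with matching wording in Protocol 10.3.6.1.1:

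1. State that eGFR is derived centrally from recorded serum creatinine, and reconcile this with SAP 4.3, which takes the value from a form.
2. For samples taken before age 18, use a height-based paediatric equation (for example bedside Schwartz) with the nearest recorded height. From age 18, use one fixed, named CKD-EPI version at all visits.
3. Compute no change from pre-treatment across a switch of equation.
4. In Table 15.2.4, show eGFR separately for participants under 18 and those 18 or over at first dose.

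The cost is SAP text and a small amount of programming. Creatinine, age, sex and, for minors, height already have a place on the CRF. There are two losses. Paediatric samples without a creatinine or a recorded height drop out of the eGFR row; this will happen, since height too is recorded only where standard care measures it. Participants who turn 18 have change calculated within one equation only.

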6. MILESTONES

| Milestone | Planned Date |
|--------------------------|------------------|
| Start of data collection | 02 February 2022 |
| End of data collection | 31 January 2030 |
| Final study report | 30 April 2030 |

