9.7. Study Data Collection

Data on participants will be collected at regular intervals and entered into the EDC system by study personnel at the study site beginning with their first dose of commercial Oxbryta® (Voxelotor). Data collection will include those data that are recorded in the participant's medical records/other secondary data sources and based on assessments performed as part of the participant's SOC. Study data that are not available in medical records or other secondary data sources will not be solicited from participants. The data to be collected in this study and target timepoints for data collection and entry are specified in the schedule of activities (SOA) in [Appendix 1](#).

There are not any required study procedures or assessments beyond the SOC. The SOA should be used as a guide for what data to enter and not for what assessments to perform. Therefore, if an assessment listed in the schedule of activity of the protocol is considered standard of care, the sites are asked to enter the assessment result into the study database. If an assessment is not conducted as SOC, the sites can just leave the relevant data fields blank.

Since Health-Related Quality of Life Measures (PROMIS, PGIC, NPRS and CGIC) are not commonly conducted as SOC, in order to allow important quality-of-life data to be gathered in the registry, questionnaires are provided to the sites and participants, and we recommend (but not require) the sites to perform these assessments.

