4.7. Statistical methodology and analyses

The following general analysis will be followed for this study, unless otherwise specified.

Unless otherwise specified, continuous/quantitative variables will be summarized using descriptive statistics which will include the number of participants with data to be summarized (n), mean, standard deviation (SD), median, first and third quartile (Q1, Q3), minimum, maximum, and the number of missing observations. Minimum and maximum will be reported with the same number of decimal places as collected in raw data, while mean, median, Q1, Q3 will be reported with one extra decimal place, and SD will be reported with two extra decimal places. Descriptive statistics for categorical/qualitative variables will be presented with number of participants and percentage (%) of participants in each category.

Percentages will not include the missing category and will be calculated over the number of participants with available (non-missing) data. A category with a zero count will be presented as “0” and a category with a 100 percentage will be displayed as “100”.

The annualized incidence rate is defined as total numbers of a given event for all participants divided by the total patient-year where the total patient-year is defined as the sum of total duration (years) as defined in the Section 4.7.1 for all participants.

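### CGIC is pooled by visit although participants may consent after any time on drug, so a trend across visits may partly compare different people

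*SAP*

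**What the plan says.** SAP 4.7.3 gives the whole CGIC analysis in one line: "The CGIC will be summarized as numbers and percentages by visit for each response category". SAP 4.7 sets the denominator: "Percentages will not include the missing category and will be calculated over the number of participants with available (non-missing) data". Each visit therefore has its own set of contributors.

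SAP 4.1 admits two kinds of participant: "Any participant who is currently taking Oxbryta® (Voxelotor) or has been prescribed and will initiate treatment with Oxbryta® (Voxelotor), is eligible to participate". The follow-up clock starts at first dose: "Regardless of how long participants have been on Oxbryta® (Voxelotor) when they enroll in the study, participants will be followed for up to 5 years". The same section says that participants "will sign the informed consent form (ICF) or assent prior to any data collection for the study". Protocol 9.7 says of the HRQoL measures, CGIC included, that they "are not commonly conducted as SOC". The study supplies the questionnaires and recommends them without requiring them.

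The schedule of activities (Protocol Appendix 1) places CGIC at months 3, 6, 9, 12, 18, 24, 30, 36, 42, 48, 54 and 60. The CGIC form asks about change since before treatment, so a long-term user can be rated for the first time at a late visit.

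The SAP does not define a visit for this table and gives no visit windows or data cut-off. SAP 4.7.1 puts the index date at consent. None of the subgroups in SAP 4.2.1 or 4.7.5 separates participants by treatment status at consent.

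**The concern.** A participant who has been on drug for t months at consent will usually have no CGIC for any visit before month t, because nobody was asking. That person joins the table at the first visit after consent. Someone who starts drug at enrolment can contribute from month 3. If the visit axis is time since first dose, the people behind the percentages change along it.

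This is delayed entry and is separate from non-response. The missing early ratings belong to people who were not yet under observation, so better completion among enrolled participants would not supply them. Those who enrol as current users have also, by definition, remained on drug until consent.

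With PROMIS dropped from the report (SAP 4.7.3), PGIC and CGIC are the only HRQoL tables in SAP Appendix A. A percentage improved that moves across visits would naturally be read as a change with time on drug, when part or all of it could be a change in who is being rated.

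**Working it through.** The plan gives no figure to reproduce: SAP 4.5 states that there is no formal sample size calculation. The check uses date arithmetic followed by an illustrative simulation.

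**Who can contribute at a visit.** For first dose F, consent C and data cut-off X, a CGIC rated at month v is possible only if C ≤ F + v ≤ X. For a new starter F is at or after C, so v cannot exceed X − C.

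**Dates** (days ÷ 30.4375). Data collection starts on "02 February 2022" (Protocol 6).
- To SAP version 3, 24 January 2025: 1,087 days = 35.7 months.
- To the planned end of data collection, 31 January 2030: 2,920 days = 95.9 months.

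The documents state no cut-off, so both dates are assumptions.
- *Cut near SAP version 3:* new starters reach months 3 to 30. They miss month 36 by 36 − 35.7 = 0.3 months, which a visit window could absorb. They cannot reach months 42 to 60.
- *Cut at the 2030 milestone:* a new starter dosed up to 95.9 − 60 = 35.9 months after study start can still reach month 60.

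**Composition.** Assumptions: 30%, 50% or 70% of 500 participants already on drug at consent; enrolment uniform over 12, 24 or 33 months; current users' first dose uniform from mid-November 2019 to consent; no dropout; full completion. The share of CGIC responses that come from new starters is:

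| Visit | Cut at SAP v3 date | Cut at January 2030 |
|---|---|---|
| Month 3 | 82–97% | 82–97% |
| Month 24 | 25–75% | 36–80% |
| Month 30 | 13–56% | 32–76% |
| Month 36 | 0% | 30–74% |
| Month 60 | 0% | 30–70% |

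With the early cut, only about 9 to 25 of 500 participants contribute at month 60.

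**Effect on the percentage improved.** Further assumptions, none from the documents: half of all who start are stayers (70% improved) and half leavers (40%); leavers stop drug after a mean of 18 months; current users enrol only if still on drug; enrolment runs over 24 months; each person's status is constant; those who stop drug stay under follow-up. If a fraction s of contributors are stayers, the percentage improved is 40 + 30s.
- New starters: s = 50%, giving 40 + 15 = 55% at every visit.
- Early cut, month 36: s is about 75%, giving 62.5%. Month 48: s is about 83%, giving 64.9%.
- 2030 cut, month 60: current users have s of about 71%, giving 61.3%. With 30% current users the pooled figure is 0.7 × 55 + 0.3 × 61.3 = 56.9%. With 70% it is 0.3 × 55 + 0.7 × 61.3 = 59.4%.

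**Sensitivity.**
- With rates of 60% and 50% and the early cut, the drift is 55% at month 3, 57.5% at month 36 and 58.3% at month 48.
- With the rates reversed (40% in stayers, 70% in leavers), it falls to 47.5% at month 36.
- With visits counted from consent and 50% current users, the line is flat at about 58% from month 3 to month 30.

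**The case against.** The strongest objection is that the visit origin is inferred. The SAP's index date is consent, and the schema for a participant on treatment at consent is not shown. If visits ran from consent, the shift in composition would largely vanish. This stands as a condition on the point. The schedule and the 5-year clock make first dose the likelier reading. Under the other, each visit would mix very different durations on drug, so the split would still be informative.

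A reader might infer that late visits hold only participants already on drug at consent. The documents do not support that as a fact: under the 2030 milestone new starters can reach month 60. An early cut is plausible, because the SAP serves the final report and describes PROMIS response in the past tense, but a SAP date is not a data cut. Nor are early visits purely new starters, since anyone on drug for less than the visit month at consent can contribute.

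A reader might also infer that the percentage improved must rise. That needs people who stop drug to be rated worse, and the documents give no such data. Earlier CGIC is not ruled out either: a rating made in usual care could be entered, and whether data from the RETRO study include CGIC is not stated.

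Finally, the table is descriptive, the SAP claims only limited efficacy data, and Protocol 9.13 acknowledges several sources of bias in comparing outcomes. That limits the consequence. It does not remove it, because the by-visit layout itself presents a trend and the general caveat does not mention this mechanism.

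**Conclusion.** The point holds conditionally and is a cheap improvement. Delayed entry follows from the documents: mixed enrolment, follow-up from first dose, CGIC seldom recorded before consent, and pooling over responders with nothing to separate the two groups. If visits are counted from first dose, the mix moves from mainly new starters to a growing share of participants already on drug. With data ending near the SAP version 3 date they would be the only contributors from about month 36, and clearly from month 42. With the 2030 date, late visits are mixed.

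Under the illustrative rates the spurious drift is 7 to 10 percentage points by months 36 to 48 with the early cut (55% to 62–65%), and about 2 to 4 points with the 2030 date (55% to about 57–59%). The existence of the shift in composition does not depend on the response rates; the size and direction of the drift do.

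**What to change.** In SAP 4.7.3 and Table 15.2.8:
- State that visits are counted from first dose, and state the data cut-off.
- Tabulate CGIC by visit separately for participants who consented before or at first dose and for those already on drug at consent, with n per group at each visit.
- Add a sentence that trends over visits are to be read only within a group.

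The stratifier comes from two dates already collected, consent and first dose, so no new data are needed. The cost is smaller counts per cell, most noticeably at the latest visits. PGIC (Table 15.2.7) has the same by-visit layout and could take the same split, though its form refers to the start of the study and not to the time before treatment.
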